IEC	Independent Ethics Committee
IMP	Investigational Medical Product
IOP	Intraocular pressure
IRB	Institutional Review Board
ITT	Intent-to-Treat
logMAR	Logarithmic Minimum Angle of Resolution
MedDRA	Medical Dictionary for Regulatory Activities
NSAID	Non-steroidal anti-inflammatory drug
OD	Oculus dexter (Right eye)
OTC	Over the Counter
OS	Oculus sinister (Left eye)
PP	Per protocol
PPE	Personal protective equipment
PT	Preferred Term
SAE	Serious adverse event
SAP	Statistical Analysis Plan
SOC	System/Order/Class
SOP	Standard Operating Procedures
TEAE	Treatment emergent adverse event
UPT	Urine Pregnancy Test
US	United States
VA	Visual acuity

Summary

Study Number	AG-920-CS303	
Clinical Phase:	Phase 3	
Type of study	Safety	
Name of Investigational product:	Articaine Sterile Topical Ophthalmic Solution (AG-920)	
Duration of treatment per subject	1 day	
Objectives and Endpoints:	Primary Objective To evaluate the ocular safety of a single topical ocular administration of Articaine Sterile Topical Ophthalmic Solution (2 drops 30 seconds apart)	Primary Endpoints Visual acuity, intraocular pressure, biomicroscopy, AEs, TEAEs, SAEs, withdrawals due to TEAEs
	Secondary Objectives A subset of up to 20 subjects (with expectations that 12 receiving AG-920 and 6 receiving vehicle) will undergo specular microscopy prior to and 3 months after receiving masked study medication to evaluate the effect of AG-920 on corneal endothelial cell count (ECC).	Secondary Endpoints Mean change from baseline in corneal endothelial cell density after treatment with AG-920
Subject Population:	Healthy volunteers Exclusion criteria may be found in Section 4.2.	
Design:	Randomized, placebo (vehicle) controlled, double-masked, parallel-group. Unequal randomization (2:1 Active:Placebo)	
Visit Schedule:	Study visits will consist of: 
 • a 1-3 day Screening Period • a dosing visit (multiple timepoints over 90 minutes) • a follow-up phone call 1-4 days following dosing And 
 • a follow-up visit at 90-95 days following dosing (ONLY for the subset of subjects participating in the ECC evaluation) 	
Number of Investigational Sites:	Up to 5 US sites	
Estimated Total Sample Size:	240 total evaluable subjects; 160 AG-920; 80 Placebo.	

	A subset of up to 20 of subjects will have specular microscopy performed.

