4.3 Subject replacement

Discontinued subjects may be replaced by enrollment of additional subjects until approximately 240 evaluable subjects have completed the study.

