9.1 Primary Hypotheses

As this is only a safety study, there is no planned inferential hypothesis in this study for efficacy.

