9.2 Sample Size Considerations

The size of this study is driven by the minimal safety exposure required for an eventual regulatory marketing application.

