9.4.8 Adverse Events

Verbatim descriptions of AEs will be mapped to MedDRA thesaurus terms and be presented in a data listing. Treatment emergent AEs, those that occur after the first dose of study medication, will be summarized by treatment group using frequency counts and percentages for each system organ class (SOC) and preferred term (PT) within each SOC. Summaries will be presented separately for ocular and non-ocular AEs. These summaries will also be presented by the relationship to the Investigational Medical Product (related, unrelated) and by severity of the AE (mild, moderate, severe). Fisher's exact test will be used to test the difference in proportions of subjects with each AE between treatment groups (SOC and PT).

9.5 *Procedure for accounting for missing, unused, or spurious data*

For this safety study, only observed data will be used. This is no planned method for imputation of missing data.

9.6 *Procedure for reporting deviations from the statistical plan*

Any deviations from the statistical plan will be described and a justification given in the final statistical report.

9.7 *Data listings*

Data listings will be prepared for all data on the database.

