2.5 Sample Size Estimation

The study is intended to enroll a total of 240 subjects in a 2:1 ratio of 160 subjects for AG-920 treatment and 80 subjects for placebo. This sample size is driven by the minimal safety exposure required for a regulatory marketing application.

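### For uncommon AE terms, the protocol's term-by-term Fisher test has little ability to show harm and puts no bound on it; neither document plans a difference in AE percentages with an interval.

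*Protocol*

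**What the plan says.** Protocol 9.4.8 asks for the number and percentage of subjects with treatment-emergent AEs by SOC and PT in each arm, split into ocular and non-ocular events and also shown by relationship and severity. It then adds a single between-arm comparison, Fisher's "exact test will be used to test the difference in proportions of subjects with each AE between treatment groups (SOC and PT". It does not say whether the test is one- or two-sided, at what level, whether p-values are adjusted over terms, or what will be concluded from them.

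Arm sizes are given in the Protocol Summary as "240 total evaluable subjects; 160 AG-920; 80 Placebo", and SAP 2.5 intends to "enroll a total of 240 subjects in a 2:1 ratio of 160 subjects for AG-920 treatment and 80 subjects for placebo". Protocol 9.2 gives the reason: "The size of this study is driven by the minimal safety exposure required for an eventual regulatory marketing application". No AE rate, detectable difference or power is stated. Protocol 9.1 says "there is no planned inferential hypothesis in this study for efficacy" and is silent on any safety hypothesis.

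AEs and TEAEs are listed as primary endpoints in Protocol section 2. Protocol 9.4.1 leaves fuller description of methods to the SAP. SAP 2.9.3 and 5.3 plan AE frequencies and percentages by treatment, with no Fisher test, difference or interval. The SAP does plan between-arm ANCOVA for visual acuity, IOP and the slit-lamp score.

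**The concern.** A safety study has to say how large an excess of each event the data leave open. A p-value for each term does not do that. With 240 subjects split 2:1 and a term seen in only a few people, a non-significant Fisher result is the likely outcome even when the drug causes the event in several percent of subjects. If such a p-value stands alone beside the counts, it can be read as evidence of no difference.

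There is a second feature. At very low event rates the counts needed for p<0.05 are not symmetric between arms. A few chance cases on vehicle can cross the line while a larger number on AG-920 does not. At those rates, a list of flagged terms would be more likely to suggest an advantage for the drug than a harm, unless the plan says how the p-values are to be read.

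**Working it through.** **Inputs.** From the documents: Fisher's test for each SOC and PT (Protocol 9.4.8); 160 and 80 subjects (Protocol Summary, SAP 2.5). Discontinued subjects "may be replaced by enrollment of additional subjects until approximately 240 evaluable subjects have completed the study" (Protocol 4.3), so 160 and 80 serve as denominators. Assumed, because not stated: two-sided test, 0.05 per term, no adjustment. The plan gives no critical count or power, so there is no figure to reproduce.

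**Step 1: p-values when all cases fall in one arm.** With N cases in total, the chance that k are on AG-920 is C(160,k)·C(80,N−k)/C(240,N). The two-sided p adds the probabilities of all splits no more likely than the observed one.

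- 8 on AG-920, 0 on vehicle: the observed split has probability 0.03675. Splits with 0, 1 or 2 on AG-920 are less likely (0.00012 + 0.00209 + 0.01575 = 0.01796). p = 0.03675 + 0.01796 = 0.055.
- 9 on AG-920, 0 on vehicle: 0.02408 + (0.00004 + 0.00074 + 0.00646) = 0.031.
- 0 on AG-920, 3 on vehicle: probability 0.03611, and every other split is more likely. p = 0.036. With 2 on vehicle, p = 0.110.

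The first flagged one-arm splits are therefore 9/160 = 5.6% on AG-920 and 3/80 = 3.75% on vehicle.

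**Step 2: power to flag harm.** If the vehicle rate is zero, a flag needs at least 9 cases on AG-920, so power = P(X ≥ 9) with X ~ Binomial(160, rate). With a non-zero vehicle rate, add Binomial(160, p1) × Binomial(80, p0) over all 161 × 81 tables that have p<0.05 and a higher percentage on AG-920.

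| True rate, AG-920 vs vehicle | Chance of a harm flag |
|---|---|
| 3% vs 0% | 5.3% |
| 5% vs 0% | 40.7% |
| 5% vs 1% | 20.5% |
| 8% vs 0% | 90.0% |

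**Step 3: false flags when the true rates are equal**, by the same enumeration.

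| True rate in both arms | Flag against AG-920 | Flag in favour of AG-920 |
|---|---|---|
| 1% | <0.01% | 1.25% |
| 2% | 0.10% | 2.36% |
| 3% | 0.49% | 2.43% |
| 5% | 1.18% | 2.17% |
| 10% | 1.70% | 2.16% |
| 20% | 1.96% | 2.01% |

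**Step 4: what an interval adds.** The Newcombe interval combines the Wilson limits (l, u) of each arm. With d the difference in proportions, the lower limit is d − √[(p1−l1)² + (u2−p2)²] and the upper limit is d + √[(u1−p1)² + (p2−l2)²].

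For 8/160 the Wilson limits are 0.0256 and 0.0956; for 0/80 they are 0 and 0.0458. So d = 0.050. The lower limit is 0.050 − √(0.0244² + 0.0458²) = −0.002, and the upper limit is 0.050 + 0.0456 = 0.096. The result is +5.0 points (−0.2 to 9.6).

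**Step 5: does the interval remove the imbalance?** It does not if it is read only for whether it excludes zero.

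- 0/160 vs 3/80 gives −3.75 points (−10.5 to −0.35), which excludes zero.
- 8/160 vs 0/80 includes zero, and 9/160 vs 0/80 excludes it. The thresholds are the same as Fisher's.
- At a true rate of 1% in both arms, the Newcombe interval excludes zero in AG-920's favour 1.25% of the time and against it <0.01%. At 2% the figures are 2.45% and 0.10%.

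The gain lies in the upper limit, not in a different rule for significance.

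**The case against.** Several points on the other side have force.

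- **The test's settings are assumed.** The protocol states neither two-sidedness nor 0.05. A one-sided test for harm would give p=0.037 for 8 AG-920-only cases. If the one-sided p is doubled instead, 3 vehicle-only cases give 0.072 and the thresholds become 4 and 9. The wording, to "test the difference in proportions of subjects with each AE between treatment groups", names no direction, so two-sided is the natural reading, but it remains an assumption.
- **The size of an excess is not hidden.** Counts and percentages by arm are already required, so a reader would see 8 (5.0%) beside 0. Only the interval is missing.
- **The test may never be run**, because the SAP names none for AEs. This stands, but then neither an estimate of the difference nor a bound on it is planned.
- **Low power for rare terms follows from the design.** The trial was sized for exposure. This is true, and it is a reason not to let a non-significant p-value carry meaning.

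A reader might infer that Fisher's test is itself faulty, that it favours the drug in general, and that replacing it with an interval cures this. The calculations do not support that. Part of the 3-versus-9 gap is the 2:1 denominators. False flags in AG-920's favour stay below 2.5% at every rate computed. The two directions come close together by 10% and are nearly equal at 20%. The Newcombe interval has the same thresholds. A reader might also infer that the sponsor will report a vehicle excess as an advantage for AG-920, or non-significance as absence of harm. No text in either document says so; the plan simply does not rule it out.

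**Conclusion.** The point holds in a limited form. For uncommon terms, unadjusted Fisher p-values at 160:80 can seldom show harm (41% power for 5% versus 0%, 5% for 3% versus 0%) and give no upper bound on it, although AEs are a primary endpoint. At true rates of about 1 to 2%, false flags fall mostly in AG-920's favour. This is a property of sparse counts with 2:1 allocation and matters little for common events.

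The figures rest on a two-sided 0.05 level and 160:80. At 156:84, 158:79, 162:81, 164:76 and 165:80, 3 vehicle-only cases stay below 0.05 and 8 AG-920-only cases stay above it. The 9-case threshold is less firm: at 164:76, 9 AG-920-only cases give p=0.061. Nothing here invalidates the trial; it is a reporting weakness that should be settled before unmasking.

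**What to change.** In Protocol 9.4.8, and in SAP 2.9.3 and 5.3, which have no AE comparison to amend and so need a new sentence:

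1. For any study-eye TEAE and for each SOC and PT, present the AG-920 minus vehicle difference in the percentage of subjects with an event, with one named 95% interval method, for example Newcombe. Choose a single method in advance, since methods can differ in which sparse tables exclude zero.
2. Report the upper limit as the excess not excluded by the data.
3. If Fisher p-values are kept, state their sidedness and label them descriptive and unadjusted for the number of terms.
4. State that neither absence of a difference nor an advantage for AG-920 will be concluded from the p-values or from whether an interval excludes zero.

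The cost is a short text change in each document and one extra column in the AE tables. No new data are needed. The drawback is that wide intervals for rare terms will be visible.

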10 QUALITY CONTROL AND QUALITY ASSURANCE

10.1 Audit and Inspection

Study centers and study documentation may be subject to Quality Assurance audits during the study by the Sponsor or its designee. In addition, inspections may be conducted by regulatory authorities at their discretion.

10.2 Direct Access to Source Data Documents

Authorized representatives of the Sponsor, a regulatory authority, an IEC or IRB may visit the site to perform audits or inspections, including source data verification. The purpose of a Sponsor audit or inspection is to systematically and independently examine all study-related activities and documents to determine whether these activities were conducted, and data were recorded, analyzed, and accurately reported according to the protocol, GCP guidelines, and any applicable regulatory requirements. The Investigator should contact the Sponsor immediately if contacted by a regulatory agency about an inspection.

10.3 Clinical Monitoring

Data for each subject will be recorded in a source document and in EDC for each subject who signs an informed consent form (ICF) and is administered IMP.

In accordance with current GCP and International Conference of Harmonisation (ICH) guidelines, the study monitor will carry out source document verification at regular intervals to ensure that the data collected in EDC are accurate and reliable.

The Investigator must permit the monitor, the IEC/IRB, the Sponsor's internal auditors, and representatives from regulatory authorities' direct access to all study-related documents and pertinent hospital or medical records for confirmation of data contained within EDC.

Due to the COVID-19 Pandemic, remote monitoring visits may replace some of the onsite monitoring visits. It will still be the responsibility of the monitor to discuss the study and any issues with the Principal Investigator via telephone or videoconference.

10.4 Data Management and Coding

The CRO will be responsible for data management per their SOPs. This will include setting up a relevant database and data transfer mechanisms, along with appropriate validation of data and resolution of queries. Data generated within this clinical study will be handled according to the relevant standard operating procedures of the data management and biostatistics departments of the CRO.

All data for subjects who sign an ICF and receive a dose of IMP will be recorded via EDC. Subjects who are screened but found ineligible for the study and who do not receive IMP will be considered screen failures. The reason for exclusion from the study will be recorded.

Study centers will enter data directly into the EDC via a secure internet connection. Data entered into EDC must be verifiable against source documents at the study center. Data recorded directly into EDC, if any, will be identified and the EDC will be considered the source document. Any

changes to the data entered into the EDC system will be recorded in the audit trail and will be FDA Code of Federal Regulations (CFR) 21 Part 11 compliant.

MedDRA will be used to code AEs. Medications will be coded by WHODrug. Missing or inconsistent data will be noted within the EDC system and queried with the Investigator for clarification. Subsequent modifications to the database will be documented.

11 ETHICAL CONSIDERATIONS AND COMPLIANCE WITH GOOD CLINICAL PRACTICE

11.1 Independent Ethics Committee or Institutional Review Board

Before initiation of the study at each study center, the protocol, the ICF, other written material given to the subject, and any other relevant study documentation will be submitted to the appropriate IEC/IRB. Written approval of the study and all relevant study information must be obtained before the study center can be initiated or the IMP released to the Investigator. Any necessary extensions or renewals of IEC/IRB approval must be obtained for changes to the study such as amendments to the protocol, the ICF or other study documentation. The written approval of the IEC/IRB together with the approved ICF must be filed in the study files.

The Investigator will report promptly to the IEC/IRB any new information that may adversely affect the safety of the subjects or the conduct of the study. The Investigator will submit written summaries of the study status to the IEC/IRB as required. On completion of the study, the IEC/IRB will be notified that the study has ended.

11.2 Regulatory Authorities

Relevant study documentation will be submitted to the regulatory authorities of the participating countries, according to local/national requirements, for review and approval before the beginning of the study. On completion of the study, the regulatory authorities will be notified that the study has ended.

11.3 Ethical Conduct of the Study

The Investigator(s) and all parties involved in this study should conduct the study in adherence to the ethical principles based on the Declaration of Helsinki, GCP, ICH guidelines, and the applicable national and local laws and regulatory requirements.

11.4 Written Informed Consent

The process of obtaining informed consent must be in accordance with applicable regulatory requirement(s) and must adhere to GCP.

The Principal Investigator(s) at each center will ensure that the subject is given full and adequate oral and written information about the nature, purpose, possible risk, inconveniences, and potential benefit of the study. Subjects must also be notified that they are free to discontinue from the study at any time. The subject should be given the opportunity to ask questions and allowed time to consider the information provided. The subject should be given every opportunity to ask for clarification of any points s/he does not understand and, if necessary, ask for more information. The subject will be required to sign and date the ICF. After signatures are obtained, the ICF will be kept and archived by the Investigator in the Investigator's study file. A signed and dated copy

of the subject ICF will be provided to the subject. The Principal Investigator(s) must maintain the original, signed ICF.

The Investigator is responsible for ensuring that no subject undergoes any study-related examination or activity before the subject has given written informed consent to participate in the study.

It should be emphasized that the subject may decline to participate in the study and may withdraw from the study at any time without consequences for their further care or penalty or loss of benefits to which the subject is otherwise entitled.

If new information becomes available that may be relevant to the willingness of the subject to continue in the study, a new ICF will be approved by the IEC(s)/IRB(s) (and regulatory authorities, if required). The subject will be informed about this new information and reconsent will be obtained.

11.5 Subject Confidentiality

Monitors, auditors, and other authorized agents of the Sponsor and/or its designee, the IEC(s)/IRB(s) approving this research, as well as that of any other applicable agency, will be granted direct access to the study subjects' original medical records for verification of clinical study procedures and/or data, without violating the confidentiality of the subjects to the extent permitted by the law and regulations. In any presentations of the results of this study or in publications, the subjects' identity will remain confidential.

12 DATA HANDLING AND RECORD KEEPING

All procedures for the handling and analysis of data will be conducted using good computing practices meeting ICH and U.S. Food and Drug Administration (FDA) guidelines for the handling and analysis of data for clinical trials.

12.1 Data quality control and reporting

After data have been entered into the study database, a system of computerized data validation checks will be implemented and applied to the database. Query reports pertaining to data omissions and discrepancies will be forwarded to the clinical Investigator and the Sponsor for resolution. The study database will be updated by the clinical investigator or their staff, in accordance with the resolved query reports. All changes to the study database will be documented.

12.2 Inspection of Records

American Genomics or designee will be allowed to conduct site visits to the investigation facilities for the purpose of monitoring any aspect of the study. The Investigator agrees to allow the monitor to inspect the drug storage area, IMP stocks, drug accountability records, subject charts and study source documents, and other records pertaining to study conduct.

12.3 Records retention

Essential documents are those documents that individually and collectively permit evaluation of the study and quality of the data produced. After completion of the study, all documents and data relating to the study will be kept in an orderly manner by the Investigator in a secure study file. This file will be available for inspection by the Sponsor or its representatives. Essential documents

should be retained for 2 years after the final marketing approval in an ICH region or for at least 2 years from the discontinuation of clinical development of the investigational product. It is the responsibility of the Sponsor or its representatives to inform the study center when these documents no longer need to be retained. The Investigator must contact the Sponsor before destroying any study related documentation. In addition, all subject medical records and other source documentation will be kept for the maximum time permitted by the hospital, institution, or medical practice.

12.4 Amendments to the protocol

Modifications of the signed protocol are only possible by approved protocol amendments and with the agreement of all responsible persons. The procedure for approval of a protocol amendment is identical to that for approval of the protocol. The ethics committee must be informed of all protocol amendments and should be asked for its opinion as to whether a full re-evaluation of the ethical aspects of the study is necessary by the committee. This should be fully documented.

The investigator must not implement any deviation from or change to the protocol, without discussion with, and agreement by American Genomics, LLC and prior review and documented approval/favorable opinion of the amendment from the relevant ethics committee, except where it is necessary to eliminate an immediate hazard to study subjects, or where the change(s) involves only logistical or administrative aspects of the study (e.g., change in monitor(s), change of telephone number(s)).

Protocol amendments will be submitted to the appropriate authority(ies) as required by the applicable regulatory requirement(s).

